5.7 Patient Identification

Study patients will be identified by a number and their initials.

The initials of the study patient will be obtained starting with the first letter of the name, followed by the first letter of the first surname and the first letter of the second surname, obtaining a maximum of three letters, in case the person has two names or a compound surname, the first letter will always be used.

Example:

To. [name] B. [name]

[figure not shown]
to. Initials: AMC

b. Initials: JDO

At the counting visit, the participant number will be assigned consecutively, using 3 consecutive digits. Once the patient has been selected, they will be assigned a number with which they will be identified throughout the study. This code will be made up of eight numbers in the following order from left to right:

- three digits of the molecule under study according to the name by the sponsor.
- Two digits corresponding to the research centre number.
- three digits of the number following their inclusion assigned in the research centre.

Example:

6. Investigational Product

6.1 Managed Products

6.1.1 Investigational Product

- Generic name: Sodium hyaluronate / Chondroitin sulfate.
- Distinctive name: Humylub Ofteno® PF.
- Active ingredients: Sodium hyaluronate 0.1% / Chondroitin sulfate 0.18%.
- Pharmaceutical form: Ophthalmic solution.
- Presentation: multi-dose dropper bottle, 10 mL.
- Prepared by: Laboratorios Sophia, S.A. de C.V.
- Solution description: Transparent solution, free of visible particles.
- Packaging description: White bottle made of low-density polyethylene with system Novelia® filled to 10 mL.

6.1.2 Reference product

- Generic name: 0.15% sodium hyaluronate.
- Distinctive name: Hyabak®.
- Active ingredients: Sodium hyaluronate 0.15%.
- Pharmaceutical form: Ophthalmic solution.
- Presentation: multi-dose dropper bottle, 10 mL.
- Prepared by: *Laboratoires Théa*, Clermont-Ferrand, France.
- Solution description: Transparent solution, free of visible particles.
- Packaging description: Abak® multidose bottle of 10ml.
- Generic name: Sodium hyaluronate
- Distinctive name: Lagricel Ofteno® PF.
- Active ingredients: Sodium hyaluronate 0.4%
- Pharmaceutical form: Ophthalmic solution.
- Presentation: multi-dose dropper bottle, 10 mL.
- Prepared by: Laboratorios Sophia, S.A. de C.V.
- Solution description: Transparent solution, free of visible particles.

- Packaging description: White bottle made of low-density polyethylene with Novelia system® filled to 10 mL.

6.1.2.1 Justification of the reference product

Hyabak® is a preservative-free lubricant manufactured by Théa Laboratories, which is indicated for the treatment of SOS. [37] It is composed of 0.15% HS and is packaged in a multi-dose bottle. It is currently a direct commercial competitor of Humylub Ofteno® PF and Lagricel Ofteno® PF.

As it is composed of HS, it shares with the products of Laboratorios Sophia, S.A. de C.V. already mentioned, some of the benefits that it can offer to patients diagnosed with SOS. However, it lacks the association with CS as in the case of Humylub Ofteno® PF, and the properties attributed to a higher concentration of HS, as in Lagricel Ofteno® PF.

On the other hand, Lagricel Ofteno® PF is an ocular lubricant also manufactured by Laboratorios Sophia, S.A. de C.V. It has a broad safety profile from its development phase to the pharmacovigilance to which it has been subjected since its international commercialization, both in its single-dose presentation and in its multi-dose version, both free of preservatives.

6.1.3 Dosage of investigational product

One QID drop, with a minimum interval of 3 hours between applications, for 30 days.

6.1.3.1 Dose justification

The dosage of treatment for SOS based on ocular lubricants will depend on the severity of the clinical picture. In the case of this study, as these are patients diagnosed with mild to moderate SOS, a dose of 4 lubricating drops per day will be used in accordance with the dosage stipulated in the prescribing information of Humylub Ofteno® PF and Lagricel Ofteno® PF. In both cases, it is indicated to apply every 4 – 6 hours. On the other hand, the Hyabak® insert refers to a dosage of 1 drop in each eye as often as necessary. [37]

The requirement to wait at least three hours between each application is added to distribute the dosage throughout the day, ensuring the protection of the ocular surface during waking hours.

6.2 Storage and handling of research products at the study site

The delivery will be made by means of a courier service contracted by the sponsor, expressly selected for this purpose, to the address of the research center according to the study plan.

The reception will be carried out by the assigned personnel of the research team. You will need to check that the primary packaging (box) is in good condition. If you show alterations or defects in its integrity that in your judgment could have damaged the content, you must report it to the sponsor. If the package does not show significant defects, it will proceed to open it.

Inside you must locate the acknowledgment document and the temperature *logger*. You must check that the temperature recorded complies with what is specified for transport and safekeeping. It will verify the content (PI) with what is reported in the document. In case the document corresponds to the content, you will sign the receipt and send it to the sponsor. Otherwise, it will notify the sponsor.

Storage and safeguarding is the responsibility of the research center. The medication must be stored in a secure area with restricted access.

The storage temperature should be less than 25°C. This limit is stipulated as described in the Hyabak® comparator product information, since Humylub Ofteno® PF and Lagricel Ofteno® PF require to be kept at a temperature below 30°C. [37]

The research center is obliged to record, in the designated format, the temperature recorded in the *data logger*, every day while the protocol is in force and has PIs. These data will be reviewed by the clinical monitor according to the record in the data logger.

In the event of loss of material, it must be documented in the logbook of inputs and outputs along with a clear description of the mechanism by which the loss occurred.

Upon completion of the protocol, all study material will be retrieved by the sponsor as part of the closing audit. The final delivery of material will be made by the principal investigator (PI) or the person designated by him to deliver material at the end of the study.

The sponsor reserves the right to initiate civil and criminal action against the PI in the event of a lack of undocumented material at the conclusion of the study.

6.3 Concomitant treatments and medications not approved during the study

The use of concomitant medications by any route of administration will not be allowed during the intervention period. Except those specified for study procedures and the use of hormonal contraceptives in women of childbearing potential. The objective of this restriction is to avoid drug interactions that could alter the results of the variables evaluated.

Allowed medications:

- Ophthalmic:
 - o Tetracaine 0.5%
 - o Tropicamide 0.8% /Phenylephrine 5%

6.4 Procedure for monitoring and measuring adherence

For more than four decades, there has been a lot of research on the appropriate way to measure and quantify medication adherence, but none has reached a consensus to stand as the gold standard, both in cross-sectional and longitudinal studies.

[38] [39] [40] [41] [42] [43] [44] [45]

There are different procedures to measure adherence to pharmacological interventions. The most common procedure includes self-reports, which include patient interviews, questionnaires and self-monitoring diaries. Its strengths are speed, flexibility, low cost and ease of implementation; They have a high degree of specificity for non-adherence, however, the sensitivity and reliability for adherence is low. [45] [46]

The biochemical measurement of the drug, or its metabolite, is one of the methods that best confirms the use of the drug. However, in addition to raising costs and being impractical, it is of little use in the context of ophthalmic applications, since concentrations at the peripheral level could be undetectable, particularly in this study since ocular lubricants whose absorption is not expected will be evaluated. [45]

Medication counting is another way to measure adherence. Classically referred to as "pill counting," in ophthalmology it translates to the weight of the bottle. This is a simple, inexpensive, and non-invasive method. The main disadvantages of this method are: 1. The application of the medication cannot be confirmed (it may have been intentionally pulled or instilled outside the eye) and 2. It depends on the patient bringing back the medication. [45] [46]

A multi-procedure approach to measuring adherence is recommended. Because there is no measurement of ideal adherence, it is appropriate to use more than one method when trying to achieve results that resemble reality. Selecting two or more methods allows their strengths and weaknesses to be compensated, to more accurately capture adherence levels. [44] There is no standardized parameter to define adequate adherence, it must be defined and delineated by the objectives of the research. [45]

Considering all the antecedents presented above, for this study adherence will be measured by the weight of the bottle and the record of applications of the patient's diary. A patient will be considered to comply with the required adherence if they have a positive record of applications in the patient's diary of at least 80%; as well as at least 65% of the decrease in the expected weight of the bottle used.

The evaluation of adhesion by means of the weight of the bottle will be carried out as follows, considering the following information: the weight of the drop, the initial weight of the container, the final weight of the container and the calculation of the total applications. The following simplified formula shall be used:

$$Ad = \frac{(P_i - P_f) 100}{PT}$$

Where:

Ad = adherence

Pi = Initial weight

Pf = final weight

PT = Total treatment weight

$$P_T = (P_g)G$$

Where:

Pg = weight of one drop of the intervention, determined by the research and development department

G = number of applications indicated for the intervention

The adherence calculation according to the patient's diary will be evaluated as follows:

$$Ad = (Ar)100/Ai$$

Where:

Ad = Adherence

Ar = Registered Applications

Ai = Applications indicated for the intervention

The research center will designate a person in charge of monitoring adherence through the diary, during the visits. The measurement of grip by weight will be the responsibility of the sponsor.

In cases where the container is not returned, or it has not preserved its physical integrity, adherence will only be measured through the patient's diary.

6.5 Strategies to improve adherence

- The PI will make the patient aware of the importance, to achieve the objectives of the study, of the correct application of the PI.
- Direct questioning by the PI about the application of the PI.
- Delivery of a printed calendar specifying the date of the visit and its activities.
- Training in the completion and review of the Patient Diary.
- If deemed necessary, text messages may be sent as reminders. The content of these messages must be previously approved by the Ethics and Research Committee (CEI).

7. Study methods and procedures

7.1 From the research centre

This study will be carried out in the research centers previously evaluated by the sponsor. These centres will be institutions or establishments where health research is carried out that complies with current regulations.

The research centers will be responsible for forming a multidisciplinary research team to execute the clinical study according to the protocol. It is their prerogative to design the organization and select the personnel who will perform the functions. However, it is the sponsor's need for the Principal Investigator (PI) to be a specialist in ophthalmology.

Any person who is designated, under their responsibility, a part of the study monitoring (co-investigator, sub-investigator, nurse, etc.) or a specific function of participation in the study (pharmacist, administrative assistant, study coordinator, etc.) must appear in the "Delegation of Responsibilities".

The competence and training of any person who has direct participation in the activities of the study must be verified prior to the performance of any activity related to the protocol. The above must be recorded and the documents that constitute evidence of this competence and/or training must be kept in the master file of the study. The competence and training of the personnel who have functions in the study, both at the central level and in the study centers, is the responsibility of the sponsor.

The sponsor must ensure that all study site personnel participating in the study are adequately trained on the study (research protocol, investigator's manual, amendments, standard operating procedures, etc.) and on the ICH (International Council for Harmonisation) GCPs, before the start of their participation in it. Training must be recorded in writing and those records must be filed in the master record of the study.

7.2 Clinical Study Registration

This clinical study will be registered by the sponsor in public clinical trial registries before its start (inclusion of the first patient): National Registry of Clinical Trials (RNPEC) of the Federal Commission for the Protection against Health Risks (COFEPRIS) and in a platform of primary registries of the World Health Organization (WHO). WHO primary registries meet specific criteria for content, quality and validity, accessibility, unique identification, technical capacity, and administration. WHO Primary Registries meet the requirements of the International Committee of Medical Journal Editors (ICMJE).

7.3 Randomization

Randomization of subjects will be carried out using a computer-based assignment system. After signing the FCI, the patient will receive a patient number with which all their information will be encrypted pseudonymity during collection and completely anonymized during analysis.

The containers will be identified by means of labels, which, in accordance with current and applicable regulations, must contain at least:

1. Sponsor's name, address, and phone number.
2. Dosage form and route of administration.
3. Batch number.
4. Legend "For clinical studies only"
5. Expiration date.

7.4 Outcome variables

7.4.1 Primary outcome variables

- OSDI score (TE: visits 1 and final).

7.4.2 Secondary outcome variables of efficacy

- Changes in the measurement of the TRLNI. (TE: visits 1 and final).
- Changes of corneal and conjunctival stains with lysmine green (ET: visits 1 and final).
- Corneal and conjunctival staining changes with fluorescein (ET: visits 1 and final).
- Conjunctival hyperemia changes (ET: visits 1 and final).

7.4.3 Safety variables

- Incidence of unexpected AEs related to the research product. (TE: Visits 1, Final and Safety Call)
- Changes in the MAVC (TE: visits 1 and final).
- Incidence of chemosis (ET: visits 1 and final).

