1.2 Synopsis

Title of the study:	
Phase IV non-inferiority clinical trial to compare the efficacy of Humylub Ofteno® PF ophthalmic solution against Hyabak® and Lagricel Ofteno® PF on the ocular surface of patients with mild to moderate dry eye syndrome	
Study number: SOPH087-0120/IV	Data created: 15-ene-20
Protocol version: 2.0	Date of version: 27-abr-20
Therapeutic indication: Ocular lubricant	Use: Dry eye
Estimated duration of the study (from the first visit of the first patient to the preparation of the final report): 12 months	Clinical development phase: IV
Objectives: Objective principal: 
 Demonstrate the non-inferiority of Humylub Ofteno® PF compared to Hyabak® and Lagricel Ofteno® PF in the efficacy of treating patients with dry eye, using the OSDI (ocular surface disease index) test score Secondary objectives: 
 Demonstrate the non-inferiority of Humylub Ofteno® PF compared to Hyabak® and Lagricel Ofteno® PF in the efficacy of treating patients with dry eye, through non-invasive measurement of tear breakup time (TBUT). Demonstrate the non-inferiority of Humylub Ofteno® PF compared to Hyabak® and Lagricel Ofteno® PF in the efficacy of treating patients with dry eye, through changes in corneal and conjunctival staining with fluorescein. Demonstrate the non-inferiority of Humylub Ofteno® PF compared to Hyabak® and Lagricel Ofteno® PF in the efficacy of treating patients with dry eye, based on changes in corneal and conjunctival staining with lysamine green. 	

 • Demonstrate the non-inferiority of Humylub Ofteno® PF compared to Hyabak® and Lagrel Ofteno® PF in the efficacy of treating patients with dry eye, based on changes in conjunctival hyperemia. • Demonstrate the non-inferiority of Humylub Ofteno® PF compared to Hyabak® and Lagrel Ofteno® PF in the safety of treating patients with dry eye, based on the incidence of chemosis. • Demonstrate the non-inferiority of Humylub Ofteno® PF compared to Hyabak® and Lagrel Ofteno® PF in the safety of treatment of patients with dry eye, based on the incidence of adverse events (AEs).
Hypotesis:
H_0 = The Humylub Ofteno® PF ophthalmic solution is not inferior in efficacy to its comparators after 30 days of treatment, showing a 35% decrease in the final OSDI test score from baseline in at least 30% of exposed patients.
$H_0: P_A - P_B \leq \delta$

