2.5 Risk-benefit assessment

2.5.1 Known potential risks

Due to the characteristics of the active ingredients of Humylub Ofteno® PF, particularly its high molecular weight and the fact that it is composed of endogenous substances widely distributed in healthy organisms, the occurrence of serious adverse effects related to the investigational product is not expected. The safety profile of both assets, both individually and in combination, has been described in other studies. See points 2.2.1.3 Safety of sodium hyaluronate, 2.2.2.3 Safety of chondroitin sulfate, and 2.3 Summary of pharmaceutical development of Humylub Ofteno® PF.

As with the rest of the topical ophthalmic application formulations, the possibility of mild and transient burning, SCE and blurred vision is anticipated, with a post-instillation duration of no more than one minute. The procedures involved in the execution of this study, and the medications used for them, are also safe and have been described as part of the complete ophthalmological examination.

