3.2 Secondary objectives

- To demonstrate the non-inferiority of Humylub Ofteno® PF compared to Hyabak® and Lagricel Ofteno® PF in the efficacy of the treatment of patients with dry eye, by means of the measurement of the LRLR.
- To demonstrate the non-inferiority of Humylub Ofteno® PF compared to Hyabak® and Lagricel Ofteno® PF in the efficacy of the treatment of patients with dry eye, by means of changes in corneal and conjunctival stains with fluorescein.
- To demonstrate the non-inferiority of Humylub Ofteno® PF compared to Hyabak® and Lagricel Ofteno® PF in the efficacy of the treatment of patients with dry eye, by changing corneal and conjunctival stains with lysmine green.
- To demonstrate the non-inferiority of Humylub Ofteno® PF compared to Hyabak® and Lagricel Ofteno® PF in the efficacy of the treatment of patients with dry eye, through changes in conjunctival hyperemia.
- To demonstrate the non-inferiority of Humylub Ofteno® PF compared to Hyabak® and Lagricel Ofteno® PF in the safety of the treatment of patients with dry eye, through the incidence of chemosis.
- To demonstrate the non-inferiority of Humylub Ofteno® PF compared to Hyabak® and Lagricel Ofteno® PF in the safety of the treatment of patients with dry eye, through the incidence of AEs.
- To demonstrate the non-inferiority of Humylub Ofteno® PF compared to Hyabak® and Lagricel Ofteno® PF in the safety of the treatment of patients with dry eye, by means of changes in CVAM.

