Conjunctival Hyperemia Changes	
It is defined as the simplest reaction of the conjunctiva to a stimulus, a red appearance is seen secondary to vasodilation of the conjunctival vessels of variable intensity.
	
Direct observation. Classification by Efron scale. See annex 16.3 Efron's scale.
	
Ordinal qualitative
	
Degrees: 0= Normal, 1= Very mild, 2= mild, 3= Moderate and 4= Severe
	
 • χ^2 (Chi-square) of Pearson or Fisher's Exacta • McNemar Test*
Incidence of chemosis	
It is defined as conjunctival edema resulting from an inflammatory reaction. It is classified as present or absent.
	
The evaluator will use a narrow beam of light at 60° and measure whether the conjunctiva separates by $\geq 1/3$ of the total palpebral aperture or whether it exceeds the gray line
	
Ordinal qualitative
	
Present/absent
	
 • One-way ANOVA • Pearson's χ^2 (Chi-square) or Fisher's Exact test
Incidence of AEs	
Any adverse medical event that occurs in a patient or clinical research subject who has been administered a pharmaceutical product and that does not
	
The AEs manifested during the conduct of the study will be collected using the FRCE.
	
Continuous quantitative Categorical qualitative
	
Frequency Subjects presenting EA/total number of subjects exposed. Intensity
 • Mild • Moderate • Severe Causality
	
One-way ANOVA Pearson's χ^2 (Chi-square) or Fisher's Exact test

- Probable
- Possible
- Unlikely

Changes BCVA	Spatial VA is the ability to distinguish separate elements of an object and identify them. It is quantified as the minimum angle of separation (located at the nodal point of the eye) between two objects that allows them to be perceived as separate objects	Snellen chart	Discrete quantitative	Fraction 0.6 to 2.0	ANOVA for repeated measures. • One-way ANOVA*
--------------	-----------------------------------------------------------------------------------------------------------------------------------------------------------------------------------------------------------------------------------------------------------------	---------------	-----------------------	-------------------------------	----------------------------------------------------------------

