7.4.4.1 Adverse events

An AE is any unfavorable medical appearance in a patient who is administered a PI, regardless of causal attribution.

Management of AEs will be performed as described in the Adverse Events section. See point 8 Evaluation and management of adverse events.

The PI will record in the corresponding section of the electronic case report form (FRCE) the AEs that the patients in the study may present, in addition to referring them in the clinical file.

For an adequate evaluation of AEs, in addition to directed questioning, it is necessary to perform the Comprehensive Ophthalmological Evaluation at each visit, which consists of: the ophthalmological examination of the eyelids and adnexa; anterior and posterior segment that is performed in a routine ophthalmological examination, whose procedures are not specifically included in the study variables. Posterior pole evaluation can be with direct or indirect ophthalmoscopy, with or without pharmacological mydriasis, at the discretion of the PI. An assessment of the fundus will be carried out in search of abnormalities that alter the result of the study. IOP will be measured in this evaluation, with the PI choice instrument, it should be measured after the evaluation of stains. The result of the assessment will be recorded in the clinical file. In the electronic case report form (FRCE), only the findings that are considered so by the PI will be reported as AEs.

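### The listed safety outcome counts only AEs that are unexpected and product-related, while the safety objective and the variable definition cover all AEs

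*Combined protocol and SAP*

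**What the plan says.** The outcome list in section 7.4.3 gives the adverse event variable as "Incidence of unexpected AEs related to the research product", assessed at visit 1, the final visit and the safety call. The synopsis carries the same entry. To count, an event must be both unexpected and related.

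The rest of the protocol is broader:

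- **Objective (3.2).** Non-inferiority is to be shown "in the safety of the treatment of patients with dry eye, through the incidence of AEs". The synopsis objective is likewise unrestricted.
- **Variable table (7.4.4).** The variable is named simply as the incidence of AEs. Operationally, "The AEs manifested during the conduct of the study will be collected using the FRCE", and the frequency is "Subjects presenting EA/total number of subjects exposed". Causality is graded from probable down to unlikely.
- **Definition (7.4.4.1, repeated in substance in 8.2).** "An AE is any unfavorable medical appearance in a patient who is administered a PI, regardless of causal attribution".
- **Analysis (10.1.2).** AEs are reported on all randomized subjects, and the adverse event row of Table 3 carries no filter for expectedness or cause.

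Section 2.5.1 states that "the possibility of mild and transient burning, SCE and blurred vision is anticipated" after instillation, lasting no more than a minute.

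**The concern.** An outcome list is where a reader looks to learn what will be counted. Here it names a subset of events, while the objective it should serve concerns all of them. An analyst who follows 7.4.3 and one who follows 7.4.4 would calculate different incidences, and nothing in the protocol says which governs.

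The narrower version also has weaknesses of its own. It brings in two classifications that an all-AE count does not need. Relatedness may be assigned directly by the investigator from clinical experience (8.4.4), in a trial that is open-label (4.1, 4.2). Expectedness has no reference document for this outcome. The only definition of unexpected is in section 8.5, and it was written for unanticipated problems.

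What is at stake is whether the reported result answers the stated safety objective. A non-inferiority statement based on the listed outcome would concern a different quantity from the one in section 3.2.

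**Working it through.** This point rests on no sample size, power or alpha figure, so there is no figure of the plan's to reproduce. The check sets the texts side by side and adds a short illustration.

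**Step 1. What each place counts**

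| Place | Limited to unexpected? | Limited to related? |
|---|---|---|
| Outcome list, 7.4.3 | Yes | Yes |
| Outcome list, synopsis | Yes | Yes |
| Objective, synopsis | No | No |
| Objective, 3.2 | No | No |
| Variable table, 7.4.4 | No | No (grades run down to unlikely) |
| AE definition, 7.4.4.1 and 8.2 | No | No |
| Analysis, 10.1.2 and Table 3 | No | No |

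The restriction appears in both outcome lists, so it is not a single slip. It appears nowhere else.

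**Step 2. How three kinds of event would be classified**

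| Event | Under 7.4.3 | Under 3.2 and 7.4.4 |
|---|---|---|
| Mild, brief burning after a drop (anticipated in 2.5.1), recorded as an AE | Not counted | Counted |
| Any AE judged unrelated to the product | Not counted | Counted |
| Hyperemia of grade 3 (an AE under 7.4.4.7, not listed in 2.5.1), judged related | Counted, if classed as unexpected | Counted |

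The two readings agree only on the third row, and there only if the event is classed as unexpected.

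**Step 3. Size, as an illustration only**

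- Input from section 2.3: in the phase I study, 14 of 30 subjects had AEs, and 14/30 = 46.7%, as stated there. These were healthy subjects, pooled over three products.
- Input from section 10.2.1: 60 patients per arm.
- Assumption: the phase I rate applies here. All-AE count per arm = 60 × 14/30 = 28.
- Let s be the share of subjects with an AE who have at least one that is both unexpected and related. The documents do not give s. Count under 7.4.3 = 28 × s.

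| s (assumed) | Patients per arm under 7.4.3 | Incidence |
|---|---|---|
| 0% | 0 | 0% |
| 10% | 2.8 | 4.7% |
| 25% | 7 | 11.7% |
| 50% | 14 | 23.3% |
| 100% | 28 | 46.7% |

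The gap between the two incidences therefore runs from zero to the whole all-AE rate, and the documents do not narrow it.

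**The case against.** The strongest reply is that the operative text already covers all AEs. Section 10.1.1 sends the analyst to 7.4.4 for the variables, not to 7.4.3. The table there, the definitions, the analysis population and Table 3 are all unrestricted, and sections 8.4 and 8.4.3 put AEs in the final report. On this view the outcome list carries a poor label and little else. Much of this stands: no AE is lost from the data. It does not settle the point, because the restricted entry is the declared safety outcome in two places and no text gives 7.4.4 precedence.

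A reader might infer more than the documents support:

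- **That every expected reaction is dropped.** This is too absolute. If the wording in section 8.5 were borrowed, an anticipated reaction of unexpected severity or frequency would still count.
- **That the listed outcome would be close to empty.** No source supports this. Several findings declared to be AEs are not among the reactions anticipated in 2.5.1: an OSDI rise of 40% or more (7.4.4.2), staining of grade III or higher (7.4.4.5, 7.4.4.6) and hyperemia of grade 3 or higher (7.4.4.7). Chemosis and visual acuity are also separate safety variables.
- **That the excluded events are the ones on which lubricants differ.** The phase IV study in section 2.3, with 326 patients, found no group differences in burning or foreign body sensation.
- **That the restriction biases towards no difference.** Attribution with the product known could favour either arm. The sponsor's pharmacovigilance unit may also apply a scored algorithm (8.4.4), and knowledge of the product can affect reporting of all AEs too.

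**Conclusion.** The plan is internally inconsistent on its adverse event outcome. As written, the entry in 7.4.3 and the synopsis does not answer the safety objective in 3.2. It leaves out AEs judged unrelated and reactions of the kind and severity anticipated in 2.5.1, and it depends on an unblinded relatedness judgement and an undefined term. The defect lies in which incidence answers the objective, not in what is collected.

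The size is unknown. The illustration of 28 patients per arm against 0 to 28 rests on a rate from healthy subjects on partly different products and on an assumed share. It shows only that the two definitions can diverge widely. The documents support no conclusion about power or about the direction of any bias. Because the conflict concerns a secondary safety objective and is easily corrected, it should be put right, but it does not threaten the primary comparison.

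**What to change.** In section 7.4.3 and the synopsis, replace the entry with the proportion of exposed subjects who have at least one AE, regardless of expectedness or causality, to match 3.2 and 7.4.4. Report related AEs, and unexpected related AEs, as subsets of that count. Tie the term unexpected to a named reference document so that the subset can be reproduced.

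In the same edit, state the denominator once: 7.4.4 and 10.1.3 use exposed subjects, while 10.1.2 refers to all randomized subjects.

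The cost is wording only. All AEs and their causality grades are already collected, so no new procedure, visit or patient is needed.
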